5.2. Secondary Objectives Analysis

5.2.1. All adverse events

The occurrence rate of adverse events from ICF signature to end of study will be compared between the treatments groups in safety set population.

5.2.2. Adverse Event Summary

An overview table of TEAEs will be provided summarizing the number (%) of subjects and number of events by any, seriousness, severity, possibly drug related TEAEs. The numbers and percentages of subjects who experienced the events and the number of events will also be

summarized by SOC and PT and by PT only. Subjects will appear in the tables only once per SOC and PT. Tables with events summarized by SOC and PT will be sorted alphabetically by SOC and then by descending frequency of PT in the "Overall" column, and tables with events summarized by PT only will be sorted by descending frequency of PT in the "Overall" column. The summary will be presented for all TEAEs, serious TEAE, severity and possibly treatment related TEAE.

5.2.3. Laboratory Safety results

Changes from baseline at D5, M1 and M4 of haematology and blood chemistry parameters results will be presented by treatment group in the SS as well as shift tables from baseline. The changes will be summarized using mean, standard deviation, median, interquartile range (Q1-Q2) and range (minimum – maximum).. Boxplots on the change from baseline and scatterplots of baseline values by time point and treatment group will be generated for each laboratory parameter. The boxplot of each treatment group will be plotted side-by-side at each time point.

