## 2.1.2. Secondary objectives

- To assess safety of acoziborole versus placebo in:
  - Haemato-biochemistry
  - Electrocardiogram (ECG) data at Day 5 (double delta versus baseline and time, age and sex matched comparison)
- To assess blood PK at Day 5 and Month 1

• To assess correlation between  $\Delta QTc$  measurements and acoziborole concentrations in blood at Day 5

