## 2.2.2. Secondary endpoint(s)

- Occurrence of adverse events (AEs) from ICF signature to the EoS
- Change from baseline in ECG parameters, biochemistry and haematology
- Blood concentration of acoziborole at Day 5 and Month 1
- ΔQTc measurements at Day 5
- Placebo-corrected change from baseline in ECG parameters (double delta [ΔΔ] heart rate [HR], ΔΔRR, ΔΔPR, ΔΔQRS, ΔΔQT and ΔΔQTc)
- Incidence of abnormal values and morphological findings in ECG at Day (D)5

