## 10.7.2. Secondary endpoint analysis

The secondary objectives are to compare safety laboratory and ECG data among the acoziborole and placebo groups. Data will be analysed using double delta analysis versus

baseline and will use time, age- and sex-matched comparisons.

The secondary endpoints are the occurrence of AEs from the time that subjects provide written informed consent to the EoS and changes from baseline in ECG and laboratory safety test results (biochemistry and haematology) to the EoS.

The majority of measured parameters are quantitative and the change from baseline will be the difference between two values. For parameters with binary outcomes (presence or absence), contingency tables (before versus after treatment) will describe the change (or not) of status.

No adjustment for multiplicity of symptoms or laboratory results is planned. The results will therefore not be confirmatory but considered as a signal of potential effect.

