1.1.1.5. Secondary endpoints

- Occurrence of adverse events (AEs) from ICF signature to end of study (EoS)
- Change from baseline in ECG, biochemistry, haematology.
- Blood concentration of acoziborole at D5 and M1
- Placebo-corrected change from baseline in ECG parameters (double delta [$\Delta\Delta$] heart rate [HR], $\Delta\Delta$ RR, $\Delta\Delta$ PR, $\Delta\Delta$ QRS, $\Delta\Delta$ QT and $\Delta\Delta$ QTc)
- ΔQTc measurements from baseline to Day 5
- Incidence of abnormal values and morphological findings in ECG at D5

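### The haematology and biochemistry objective is stated against placebo, but the SAP prespecifies no between-arm estimate or interval for the laboratory parameters, and the protocol is not uniform on whether double delta covers them.

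*SAP*

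**What the plan says.** **Objective.** Protocol 2.1.2 opens its secondary objectives with "To assess safety of acoziborole versus placebo in" and lists haemato-biochemistry first. SAP 1.1.1.2 repeats this.

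**Protocol analysis text.** Protocol 10.7.2 begins: "The secondary objectives are to compare safety laboratory and ECG data among the acoziborole and placebo groups". The next sentence reads "Data will be analysed using double delta analysis versus" baseline, and calls for comparisons matched on time, age and sex. Neither sentence is limited to ECG. The same section says no multiplicity adjustment is planned and that the results are signals rather than confirmatory findings.

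**Protocol text pointing to ECG only.** In Protocol 2.1.2 the double delta wording sits in the ECG bullet: "Electrocardiogram (ECG) data at Day 5 (double delta versus baseline and time, age and sex matched comparison". Protocol 2.2.2 names "Placebo-corrected change from baseline in ECG parameters" and has no matching entry for laboratory data. The analysis of covariance for the placebo-corrected change appears under the ECG heading within Protocol 10.7.2.

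**SAP.** The endpoint in SAP 1.1.1.5 is "Change from baseline in ECG, biochemistry, haematology", without placebo correction. SAP 5.2.3 says: "Changes from baseline at D5, M1 and M4 of haematology and blood chemistry parameters results will be presented by treatment group in the SS". It adds shift tables, then: "The changes will be summarized using mean, standard deviation, median, interquartile range (Q1-Q2) and range (minimum – maximum". Boxplots and scatterplots complete the section.

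**The concern.** The objective is comparative, and one sentence of the protocol's analysis section names a comparative method for it. The protocol refers the reader to the SAP for full statistical detail, and the SAP section that should carry the comparison is purely descriptive.

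Two things follow if the SAP is applied as written.

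- Drift common to both arms has to be separated from a drug effect by inspecting adjacent columns and boxplots. Protocol 1.4 shows why this matters. It reports transaminase increases in the healthy-volunteer study and suggests that some abnormalities there reflected fluctuations unrelated to drug, picked up over a long follow-up.
- SAP section 1 says that analyses not described in the SAP will be reported as post hoc. A laboratory contrast that Protocol 10.7.2 appears to plan would then be labelled post hoc, or not be done.

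**Working it through.** **1. Does any other part of the SAP supply the contrast?**

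| Place | Content | Supplies a laboratory contrast? |
|---|---|---|
| SAP 3.1 | 95% CIs for all estimates | No; it defines no laboratory estimate |
| SAP 5.2.1 | AE rates compared between arms | No; AEs only |
| SAP 5.2.3 | Laboratory changes presented by arm | No |
| SAP 5.2.5 to 5.2.7 | ECG, blood concentration and exposure-response deferred to separate reports | No; laboratory data are not deferred |
| SAP 5.2.8 | Signs and symptoms compared with placebo | No |

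The SAP says so where it intends a comparison (5.2.1, 5.2.8). For laboratory data it says only that results are presented.

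**2. The plan's one powered double delta figure.** The documents give no laboratory SD, effect size or power, so there is no laboratory figure to reproduce. For context, Protocol 10.7.2 gives for QTc: 192 subjects, SD 12 msec, expected difference 4 msec, 90% upper bound below 10 msec, power above 90%. At 3:1 the arms are 48 and 144.

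- SE = 12 × √(1/48 + 1/144) = 2.0 msec
- Power = Φ((10 − 4)/2.0 − 1.645) = Φ(1.355) = 91.2%

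This agrees with the stated figure. Double delta is worked out for ECG and for nothing else.

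**3. Precision of the missing laboratory contrast.** The inputs are 900 and 300 subjects (SAP 2.4.1) and two-sided 5% (SAP 3.1). Results are in SD units of the change from baseline, because no laboratory SD is given.

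- SE = √(1/300 + 1/900) = 0.0667 SD
- 95% CI half-width = 1.96 × 0.0667 = 0.131 SD
- With 10% of each arm missing (assumed; 270 and 810): 1.96 × √(1/270 + 1/810) = 0.138 SD
- Detectable difference at 80% power: (1.960 + 0.842) × 0.0667 = 0.187 SD
- Detectable difference at 90% power: (1.960 + 1.282) × 0.0667 = 0.216 SD

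These figures are unadjusted. Baseline adjustment would be expected to narrow them.

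**4. Number of intervals.** Protocol 8.3.1 lists 3 haematology and 14 biochemistry parameters, 17 in all, counting the white cell count once and leaving out the differential, which is done only if the count is abnormal. With three post-dose visits (D5, M1, M4):

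- 17 × 3 = 51 intervals
- Expected number excluding zero with no drug effect: 51 × 0.05 = 2.55

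The expected count does not depend on correlation between parameters or visits, although its spread does.

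**The case against.** The strongest reply is that double delta was meant for ECG alone. The objectives bullet, the endpoint list and the covariance-model bullet all tie it to ECG. The matching phrase in Protocol 10.7.2 closely follows the ECG objective and may have been carried over. Protocol 10.7.2 also goes on to define change from baseline simply as a difference between two values, which SAP 5.2.3 delivers. This stands as far as it goes: a reader might infer that the protocol gives a settled commitment to double delta for laboratory data, and the text is too inconsistent for that. It does not close the gap, because the objective is still set against placebo in both documents and no estimate serves it.

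A reader might also infer that laboratory safety gets no comparison at all. The documents do not support this.

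- Protocol 8.3.1 and 8.5.2 require clinically significant abnormalities to be reported as AEs, or as medical history if recorded at baseline. Those that emerge or worsen after dosing enter the excess rate and the stratified test in SAP 5.1, with preferred-term comparisons at about 1% or more.
- Means and SDs by arm, with the group counts, let anyone derive an unadjusted difference and interval.

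What these routes lack is a prespecified contrast on the parameters, sensitive to shifts below the investigator's threshold for clinical significance.

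A third inference would be that the randomised 900 versus 300 comparison is thrown away. SAP 3.4.2 and 3.4.4 analyse the Safety Set by treatment received, as determined by acoziborole detection after misallocation was found. A contrast in that set would not be strictly as randomised either.

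The table shells are attached separately and were not available, so the point concerns the SAP text only.

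**Conclusion.** The point holds in a limited form. The SAP text gives no prespecified between-arm estimate or interval for any laboratory parameter, although the objective is acoziborole versus placebo, and the protocol is inconsistent about whether double delta applies. This is a gap in a secondary, signal-detection objective. It does not touch the primary TEAE analysis. It should be corrected before unblinding, so that the contrast does not have to be labelled post hoc.

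Its size is best expressed as what is left unestimated: a difference that the trial could report to within about ±0.13 SD of the change, or ±0.14 SD if 10% of values were missing. This assumes arms close to 900 and 300 by treatment received, a normal approximation and no covariate adjustment. A reader might instead try to size the point by the efficiency of ANCOVA over a change-score comparison. That does not measure the gap, because SAP 5.2.3 contains neither analysis.

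**What to change.** In SAP 5.2.3, for each haematology and biochemistry parameter at D5, M1 and M4:

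- Fit an ANCOVA of change from baseline on arm, baseline value, age and sex, in the Safety Set as already defined. Report the placebo-corrected difference with a two-sided 95% CI. Comparing arms at the same visit, with age and sex as covariates, covers the three factors that Protocol 10.7.2 names for matching. No p-value is needed.
- Label the results as non-confirmatory signal detection without multiplicity adjustment, in line with Protocol 10.7.2. State that there are 51 intervals and that about 2 to 3 are expected to exclude zero by chance.
- Keep the summaries, shift tables and plots. A difference in means can miss a few extreme enzyme or bilirubin values, and the shift tables are better suited to showing those.

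Then reconcile the protocol so that its objectives, endpoints and 10.7.2 agree on where double delta applies. If the sponsor decides to limit double delta to ECG, it should say so with a reason, and state how the placebo comparison for haemato-biochemistry will otherwise be made.

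The cost is SAP wording, a protocol clarification, routine programming and an extra column or table. All the variables are already collected. The drawback is the added number of intervals and the chance findings among them, which the labelling addresses.

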5.2.4. Vital Signs results

The baseline summary of the vital signs will be provided in the SS using descriptive summaries of actual (absolute) values and changes from baseline will be presented for Body Mass Index (BMI), axillary temperature, respiratory rate, heart rate, systolic and diastolic blood pressure and Karnofsky performance status. These tables will be grouped by treatment group, and by visit. Individual vital signs data will also be presented in a subject listing.

5.2.5. Electrocardiogram (ECG)

The analysis of electrocardiogram (ECG) data will be described and reported separately.

5.2.6. Acoziborole Blood Concentration

The analysis of PK data will be described and reported separately.

5.2.7. Exposure-Response Analysis

The analysis of PK data will be described and reported separately.

5.2.8. Change in Signs and Symptoms

The binary variable of presence or absence of signs and symptoms will be derived from the clinical examination data. The change from baseline in number (proportion) of subjects with signs and symptoms at D5, M1, M4, change at M1 from D5, and change at M4 from D5 and M1, and change will be compared between treatment and placebo group using contingency table.

5.3. Exploratory Objectives (Sub-study) Analysis

5.3.1. Exploratory Analysis

The primary set of subjects for exploratory efficacy analyses is the Safety set composed of subjects who participated in the TrypSkin sub-study. The primary exploratory objective is to establish whether acoziborole reduces the occurrence at 4 months of dermal trypanosomes in comparison with placebo. The exploratory efficacy will be evaluated using diagnostic and clinical endpoints. The primary diagnostic endpoint will be dermal trypanosome positive if TgSGP-PCR in skin is positive and the clinical endpoint will be the occurrence/presence of dermatitis and/or pruritus symptoms at 4 months. The occurrence rate of positive dermal trypanosome at 4 months based on the primary diagnostic parameters will be the primary measure of interest because the sample size is under control, and it corresponds to a measure of the level of potential transmission of reservoirs. The magnitude of the treatment effect will be the odds ratio of positive dermal trypanosomes. A Cochran Mantel Haenszel test using sites as strata will be used to compare acoziborole and placebo occurrence rate at 4 months of positive dermal trypanosome as well as occurrence of dermatitis and/or pruritus symptoms. In case of small proportions, the exact Cochran-Mantel-Haenszel (CMH) test will be performed. The Breslow-Day test of homogeneity of the odds ratio across sites will be performed to assess the generalizability of the treatment effect. If the test is significant, a forest plot will be provided to display the heterogeneity of the magnitude of treatment effect across sites and to detect sites explaining the heterogeneity.

As the odds ratio is not easy to interpret when the rate of positive subjects in the placebo group is not small ($P_0 > 0.05$), the odds ratio (OR) will be converted into the risk ratio (RR) using the following formula:

$$RR = \frac{P_1}{P_0} = \frac{OR}{(1 - P_0) + P_0 \times OR)}$$

where P_1 and P_0 are the estimated proportions of positive subjects in the acoziborole group and placebo group respectively. The excess rate $(P_1 - P_0)$ will also be estimated as a secondary measure of the magnitude of the treatment as well as the NTT (number of subjects needed to treat to get one less positive subject at 4 months in acoziborole group. The exploratory efficacy analysis results will be presented and individual data listing.

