#### Assessments on 4-month follow-up visit (end of study visit):

- Recording of concomitant medications
- Collection of AEs
- Serological test (CATT or HAT Sero-K-Set RDT, same test than the one used at baseline to be repeated)
- Collection of blood/lymph for parasitological testing
- Urine pregnancy test (women of childbearing potential only)

- Physical and clinical examination (including assessment of eventual signs and symptoms that might suggest HAT disease, vital signs, body weight and height)
- Karnofsky index
- Dermatological examination
- Blood sampling for assessment of haematology and biochemistry parameters

For subjects participating in the TrypSkin sub-study, the following assessment will be performed:

- Sampling of 3 mL fresh blood (in preservative buffer) and 5 DBS
- Sampling of two 2 mm-skin-punch biopsies on the right back shoulder under local anaesthesia

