#### Analysis of secondary clinical and diagnostic parameters

Dermal trypanosomes may be the cause of dermatitis and/or pruritus, therefore a secondary clinical and exploratory question of interest is:

Does acoziborole reduce the occurrence at 4 months of dermatitis and/or pruritus signs or symptoms in comparison with placebo?

The secondary clinical parameter will be the occurrence/presence of dermatitis and/or pruritus signs or symptoms at 4 months.

The same approach as for the primary diagnostic parameter will be used for the occurrence of dermatitis or pruritus.

Current specific molecular diagnostic methods are known to be of low sensitivity. The TrypSkin sub-study aims at testing new methods to overcome this weakness.

Secondary diagnostic parameters will be the occurrence of IHC+ results in skin, TBR-PCR+ and/or 18S-PCR+ in blood and/or skin, as well as novel diagnostic parameters corresponding to occurrence of positive results by qPCRs, multiplex RT-qPCRs and SHERLOCK in blood and/or skin.

The secondary analyses will be exactly the same as the primary diagnostic parameters.

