2.2. Randomization

Unbalanced randomization of 3:1 will be performed by blocks of size 16 to keep the allocation ratio as close as possible to the planned allocation ratio, and to get the number of randomized

subjects exposed to acoziborole as close to 900 as possible.

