2.4. Sample size and ratio determination

2.4.1. Sample size for the main study

The sample size was determined by calculation based on statistical probabilities to detect uncommon TEAEs in active group. The definition for uncommon event is a relative frequency between 0.1% and 1%. The median relative frequency is therefore 5/1000 (0.5%). The probability to detect at least 1 event if the true incidence rate is 0.5% is as high as 98% with 900 subjects and the probability is 83.5% for a true incidence rate of 2/1000 (0.2%). According to the calculations, 900 subjects exposed to acoziborole shows a high probability (>99%) of detecting at least one event (if the incidence rate is 1%) with a similar probability when exposing 1200 subjects. Therefore, 900 subjects will be administered with acoziborole and 300 subjects with placebo, for an overall sample size of 1200 subjects. The calculations were performed using StatXact 9 software and presented in Table 2.4.1.1.

A subject declared as lost to follow-up will be replaced to maintain the planned sample size. From 5 months after the start of the study, the rate of subjects lost to follow-up will be regularly assessed and recruitment will be adjusted accordingly to ensure that 1200 subjects will complete the 4 months of follow-up.

Table 2.4.1.1: Statistical probabilities for detecting uncommon treatment emergent adverse events (TEAEs) in the acoziborole group.

Objectives/Sample size	N=900	N=1200
Chance of detecting at least one event if the incidence rate is 1%	99.9%	99.99%
Chance of detecting at least one event if the incidence rate is 0.1%	59.36%	68.89%
Precision: 95% exact CI if one event is observed	0.003 – 0.6%	0.002 – 0.46%
Precision: 95% exact CI if three events are observed	0.068-0.97%	0.052-0.73%

CI=confidence interval; TEAEs=treatment-emergent adverse events

Uncommon TEAEs are those with frequency \geq 1/1000 and <1/100 as per regulatory guidelines.

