2.4.2. Sample size for the TrypSkin study

For TrypSkin sub-study, the primary objective is to estimate the prevalence of extravascular dermal *T.b. gambiense* trypanosomes in a population of seropositive subjects non-confirmed parasitologically. Preliminary results from Guinea, on a limited number of subjects, have shown that all seropositive individuals presenting a positive CATT test in plasma dilution \geq 1:4, but non-confirmed by parasitological examination of blood and lymph, had parasites in skin biopsies⁸. Knowing that approximately 25% of the RDT positive subjects non-confirmed parasitologically present a positive CATT test in plasma dilution \geq 1:4, it is hypothesized that up to 20-25% of the population of RDT-positive subjects non-confirmed parasitologically enrolled in the TrypSkin

study could possibly carry dermal extravascular parasites. Bearing in mind this higher limit of the skin-dwelling trypanosome prevalence, we have estimated the minimum sample size required to be able to evaluate the real prevalence with a satisfactory precision (a narrow CI). Under the assumption that skin-dwelling trypanosomes could be observed in up to 20-25% of the 1,200 subjects, to obtain a 95% confidence interval with a precision of 3%, a minimum of 690 evaluable subjects is required. A provision of 5% (35 subjects) is planned in case skin samplings would be non-analyzable. Overall, the number of subjects to be enrolled in the TrypSkin ancillary study is therefore 725. The determined sample size is guided by the expected precision as presented in Table 2.4.2.1.

	Estimated Prevalence								
	0.05	0.10	0.15	0.20	0.25	0.30			
0.025	300	550	780	980	1160	1300			
0.03 ^{Error!} Reference source not found.	200	390	540	690	800	900			
0.05	80	130	200	245	290	320			

Table 2.4.2.1: Sample sizes and corresponding precision for TrypSkin exploratory study

CI=confidence interval

^a Width of 95% CI approximately 0.06 (6%)

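### The Month 4 dermatitis/pruritus comparison is planned only in TrypSkin participants, although the dermatological examination is scheduled for every subject; adding the full Safety Set would narrow the interval by about 22%

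*SAP*

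**What the plan says.** - **Who is examined.** Protocol Table 1 and SAP Table 2.3.1 list the dermatological examination among the main-study rows at screening, Month 1 and Month 4. The block of TrypSkin procedures below holds only blood for molecular biology and the skin punches. The visit lists in Protocol 8.1.1 and 8.1.2.2 agree: at Month 4, "Dermatological examination" is in the list for all subjects, and the TrypSkin-only list adds blood, dried blood spots and biopsies.
- **The clinical question.** Protocol 10.8 asks whether acoziborole reduces dermatitis and/or pruritus compared with placebo: "The secondary clinical parameter will be the occurrence/presence of dermatitis and/or pruritus signs or symptoms at 4 months". It is to be analysed in the same way as the primary diagnostic parameter, that is, by a site-stratified Cochran-Mantel-Haenszel (CMH) test with odds ratio and excess rate.
- **The analysis set.** SAP 5.3.1 states: "The primary set of subjects for exploratory efficacy analyses is the Safety set composed of subjects who participated in the TrypSkin sub-study". SAP 3.4.3 requires at least one sub-study sample. Protocol 10.2 likewise limits the set to sub-study participants.
- **Sizes.** Main study: "Therefore, 900 subjects will be administered with acoziborole and 300 subjects with placebo, for an overall sample size of 1200 subjects". Sub-study: "Overall, the number of subjects to be enrolled in the TrypSkin ancillary study is therefore 725". Participation is optional, limited to participating sites, and closed to people with known diabetes or haemophilia (Protocol 3.1 and 4.2).

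**The concern.** Whether a subject has dermatitis or pruritus at Month 4 can be established without a biopsy or a PCR result. The TrypSkin set is needed for the molecular and immunohistochemical endpoints, and for relating symptoms to skin-test results. It is not needed to compare symptoms between arms. Its size was chosen to estimate the prevalence of skin parasites, not for this endpoint.

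Two other planned analyses come near the question in the full Safety Set, but neither answers it:

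- SAP 5.2.8 compares the presence of signs and symptoms between arms, but takes them from the clinical examination, which is a separate row of the schedule. It names neither dermatitis nor pruritus and plans no site-stratified CMH test, odds ratio or excess rate.
- SAP 5.1 compares preferred terms of treatment-emergent events at about 1% or more. These are events that start or worsen after dosing (SAP 3.2), and Protocol 8.5.1 does not count a condition present at the first visit that does not worsen. Baseline symptoms that persist or resolve therefore do not appear, and resolution is part of the benefit being looked for.

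At stake is the precision of one exploratory clinical result.

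**Working it through.** **Inputs**

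- Main study: 900 acoziborole and 300 placebo (SAP 2.4.1).
- Allocation: "Unbalanced randomization of 3:1 will be performed by blocks of size 16" (SAP 2.2).
- TrypSkin: 690 evaluable and 725 enrolled (SAP 2.4.2).
- Significance level: two-sided 5% (SAP 3.1).
- Rate of dermatitis/pruritus: not given in the documents, so a range is assumed.

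**The plan's own figure.** The SAP says "to obtain a 95% confidence interval with a precision of 3%, a minimum of 690 evaluable subjects is required". With n = 1.96² × p(1−p)/d², p = 0.20 and d = 0.03, n = 683, which agrees with 690 to within about 1%. Then: "A provision of 5% (35 subjects) is planned in case skin samplings would be non-analyzable", and 690 + 35 = 725. The margin of 35 is for unusable skin samples. That loss does not affect a symptom endpoint, so 725 is the right comparator, not 690 or the 700 used in the ratio table (SAP 2.4.3).

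**Subjects not used.** 1200 − 725 = 475, and 475/1200 = 39.6%.

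**Arms at 3:1.** 725/4 ≈ 181 placebo and 544 acoziborole, against 300 and 900.

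**Interval width.** With the same rate p in both arms, the half-width is 1.96 × √[p(1−p)(1/n₀ + 1/n₁)].

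- √(1/181.25 + 1/543.75) = 0.0858
- √(1/300 + 1/900) = 0.0667
- Ratio = √(725/1200) = 0.777, so the interval is about 22% narrower. The rate p cancels. The ratio also stays the same if the same share of each set attends Month 4.

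| Assumed rate | TrypSkin, 181/544 | All, 300/900 |
|---|---|---|
| 5% | ±3.7 points | ±2.8 points |
| 10% | ±5.0 points | ±3.9 points |
| 20% | ±6.7 points | ±5.2 points |

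**Power, for illustration.** Power = Φ[(|p₀ − p₁| − 1.96 × SE₀)/SE₁], where SE₀ uses the pooled rate and SE₁ the separate rates. Assume 10% on placebo, halved to 5% on acoziborole; the pooled rate is then 6.25%.

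- 181/544: SE₀ = 0.0208 and SE₁ = 0.0242, giving power of about 65%.
- 300/900: SE₀ = 0.0161 and SE₁ = 0.0188, giving power of about 84%.

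For a 30% reduction from an assumed 20%, the same formula gives 49% and 69%.

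**The case against.** The strongest defence is that the restriction is deliberate and consistent. Both documents define dermatitis/pruritus as a TrypSkin exploratory endpoint. The protocol's reason for it is mechanistic, that skin parasites may cause these symptoms, and the SAP pairs the symptoms with skin-test results (5.3.3 and 5.3.4). One set for parasite and symptom outcomes is coherent. Protocol 8.2 says the study is not designed to evaluate efficacy, and no decision rule uses this result. All of that stands. It is a reason to keep the TrypSkin analysis, but not a reason to leave out a second table.

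A second objection also stands, as a condition. Neither document describes what the dermatological examination records. Pruritus is a reported symptom, and its capture in all 1200 subjects is an inference. No TrypSkin-only skin assessment other than biopsy is listed, which supports the inference, but the CRF must confirm it.

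A reader might infer more than the documents support:

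- *The comparison is biased, because participants volunteer for biopsy or because an earlier punch affects the skin at Month 4.* Participation is decided at consent, before randomisation, and the punches are taken in both blinded arms. Selection limits only how far the result generalises, and no figure shows by how much.
- *The data outside TrypSkin are thrown away.* SAP 5.2.8 and the preferred-term comparison use part of what is known about skin symptoms in the full set.
- *The gain is 24%.* That follows from 700 subjects (√(700/1200) = 0.764), a count of evaluable biopsies that does not apply here.

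**Conclusion.** The point holds as a free improvement in efficiency for an exploratory endpoint. It is neither a contradiction nor a bias. About 475 of 1200 subjects (about 40%) are outside the planned Month 4 dermatitis/pruritus comparison. Including them would narrow the interval for the excess rate by about 22% at any event rate, or roughly one percentage point on the half-width at an assumed 10%.

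This rests on four assumptions:

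- TrypSkin reaches its target of 725. A smaller sub-study makes the gain larger, and a larger one makes it smaller.
- Month 4 attendance is similar in the two sets.
- The Safety Set is close to 1200 with arms close to 3:1. The SAP requires a PK sample and assigns arms by actual treatment, so the real counts will differ slightly.
- Both symptoms are recorded in all subjects.

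The event rates and effects above are illustrations. The documents do not support replacing the protocol-defined set, and the gain does not require it.

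**What to change.** Before unblinding, first check that the CRF records both dermatitis and pruritus at baseline and Month 4 in all subjects. If it does, add to SAP 5.3.1:

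> The Month 4 comparison of dermatitis and/or pruritus (site-stratified CMH test, odds ratio, excess rate with 95% CI) will also be made in all Safety Set subjects with a Month 4 dermatological examination, and reported beside the result in the TrypSkin set.

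If only one of the two symptoms is recorded in everyone, limit the added analysis to that symptom and say so. Keep the TrypSkin set for the molecular and immunohistochemical endpoints and for the association between symptoms and skin-test results.

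The cost is a few lines of SAP text and one table. No visit, procedure, subject or protocol amendment is needed, and every planned result is still reported. Timing matters: under the SAP introduction, an analysis not described in the SAP must be labelled post hoc in the study report.
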